 - a) This serves as a surrogate for false positive lesion detection during use of CADe
- 5) Withdrawal time when no maneuvers are performed
 - a) Limited to Provation Sites
 - b) To assess the negative impact of CADe on procedure time or a possible Hawthorne effect.
- 6) Provider satisfaction with CADe for colonoscopy
- 7) Adenoma detection rate stratified by the endoscopist's pre-CADe ADR quintile

Additional analyses to be considered (due to data availability):

- 1) Bowel preparation quality
 - a) Limited to Provation sites
- 2) Number of polyps per colonoscopy
 - a) Limited to Provation sites
- 3) Size of polyps detected
 - a) Limited to Provation sites
- 4) Advanced neoplasia detection rates
 - a) Limited to Provation sites
- 5) Surveillance recommendations after colonoscopy

Independent Variables:

- 1) VA Facility characteristics
 - a) Pre-randomization adenoma detection rate

- 2) Patient characteristics
 - a) Age
 - b) Gender
 - c) Race
 - d) Ethnicity
 - e) Rurality
- 3) Provider characteristics
 - a) Specialty
 - b) Sex
 - c) Years since completion of medical training
- 4) Colonoscopy indication (Provation sites only, if available)
 - a) Screening
 - b) Surveillance
 - c) FOBT+
 - d) Other
 - e) Unknown
- 5) Bowel preparation quality (Provation sites only, if available)
 - a) Adequate vs. inadequate
 - b) Aronchick
 - c) Boston Bowel Preparation Score

Statistical Methods:

Colonoscopies performed on the day of CADe installation and the next 5 colonoscopies performed by each endoscopist after the date of installation (or matched date for control sites) will be excluded as a washout period to minimize training adaptation. For the 26 endoscopists who performed colonoscopies at multiple facilities, we will retain only procedures at the facility where they performed the largest number of colonoscopies.

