Baseline data will be summarized as number (%), mean (\pm standard deviation) or median (interquartile range), as appropriate. For binary outcomes, we will estimate the association of CADe on study outcomes using mixed effects logistic regression (PROC GLIMMIX, SAS software, Cary, NC) with random intercepts for facility and endoscopist and random slopes (at the facility and endoscopist level) for study phase. We will also include fixed effects for group, phase, and a group by phase interaction (product term), with colonoscopy serving as the unit of analysis. The group by phase interaction is quantified as a ratio of odds ratios, where a coefficient greater than 1 for the interaction term (or 0 on the log-odds scale) reflects increased neoplasia detection in the post-deployment phase versus the pre-deployment phase in the CADe group compared to the non-CADe group. We will control for pre-randomization ADR stratum, patient demographics (e.g., sex, age, race, ethnicity and rurality), and endoscopist information (e.g., specialty, sex, years since medical degree) in all analyses.

After estimating the association of CADe on adenoma detection, we will assess whether the effect was moderated by patient and endoscopist characteristics. We will fit additional models

for each potential moderator, adding a main effect for the moderator and interactions (product terms) with group, phase, and group by phase terms as fixed effects.

Withdrawal time information will only be available from the subset of VA facilities that use Provation MD software. As withdrawal time is a continuous variable, we will use a linear mixed effects regression model with the same predictors as described above. We will include only those colonoscopies without an associated pathology report and where cecal intubation was complete.

To assess whether the effect of CADe on ADR is moderated by endoscopist ADR quintile, endoscopists with at least 100 colonoscopies in the pre- and post-deployment phases each will be divided into quintiles based on pre-intervention ADR. The quintile variable will be entered into the model described above as a main effect and an interaction (product term) with the group, phase, and group by phase terms.

References:

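### CADe allocation differed by baseline ADR stratum, but the primary model as written has no stratum-by-phase term, so the group-by-phase estimate is confounded if ADR change differs by stratum for reasons other than CADe

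*Combined protocol and SAP*

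**What the plan says.** Version 2.1, Intervention, sorts facilities into three strata by facility-level ADR (below 30%, 30 to <40%, ≥40%). About half of the facilities in the two lower strata were allocated devices. The remaining devices went to randomly selected ≥40% facilities, so that each VISN ended with two or three CADe facilities. In all, 43 facilities received CADe. No calendar window is given for the ADR used to stratify. Versions 1.0 and 1.1 (Statistical Methods) put the comparison facilities at over 100; Version 2.1 does not repeat the count.

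The primary outcome is a difference between groups in pre-to-post ADR change. The current Statistical Methods state: "We will also include fixed effects for group, phase, and a group by phase interaction (product term"; the model is fitted "with random intercepts for facility and endoscopist and random slopes (at the facility and endoscopist level) for study phase", "with colonoscopy serving as the unit of analysis". Stratum enters only in this sentence: "We will control for pre-randomization ADR stratum, patient demographics (e.g., sex, age, race, ethnicity and rurality), and endoscopist information".

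Elsewhere in the same section phase interactions are written out. The moderator models are specified as "adding a main effect for the moderator and interactions (product terms) with group, phase, and group by phase terms as fixed effects", and for endoscopist quintile "The quintile variable will be entered into the model described above as a main effect and an interaction (product term) with the group, phase" and group-by-phase terms.

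**The concern.** Where the chance of receiving CADe depends on stratum, randomization supports comparison within stratum and not between the pooled groups. The CADe group is enriched in low-ADR facilities by design. The effect of interest is a difference in change, so the adjustment has to reach change. A stratum main effect shifts both phases equally. Random phase slopes let facilities and endoscopists scatter around a common mean change; they do not absorb a mean change that differs by stratum.

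If low-ADR facilities would have risen more than others without CADe, part of that rise is credited to CADe. If they would have risen less, CADe is under-credited. One possible route is regression to the mean, if the stratifying ADR was measured over months that also belong to the pre-phase. Devices were bought in late 2022 and outcome data start October 1, 2021, so overlap is possible, but the plan does not say.

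**Working it through.** The plan gives no sample size, power, alpha or facility count per stratum, so there is no design figure to reproduce.

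**1. Allocation share (from the documents).** With C controls the overall CADe share is 43/(43 + C). For C > 100 this is below 43/143 = 30.1%. If the lower strata are at about 50%, the ≥40% stratum must lie below the overall share. With L lower-stratum facilities split evenly, its share is (43 − L/2)/(43 + C − L).

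**2. Bias with stratum as a main effect only.** If lower-stratum facilities change by an extra δ unrelated to CADe, the group-by-phase coefficient is off by about (w1 − w0)δ, where w1 = (L/2)/43 and w0 = (L/2)/C are the lower-stratum shares of the two groups.

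Assumptions: L = 10 to 40; C = 100; equal facility volume; no CADe effect; extra rise of 2 ADR points. On the log-odds scale, δ is 0.02/(0.47 × 0.53) = 0.0803 at the overall ADR of 47%, or 0.02/(0.35 × 0.65) = 0.0879 at an assumed lower-stratum ADR of 35%.

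**3. Type I error (assumed two-sided 5%).** Assume 6 endoscopists per facility, with 200 pre-phase colonoscopies each and 35% of that post-phase (1,200 and 420 per facility). The variance of a facility's change is σF² + σE²/6 + 1/(1200 × 0.249) + 1/(420 × 0.249), where 0.249 = 0.47 × 0.53.
- Small phase-slope SDs (facility 0.08, endoscopist 0.10): 0.0064 + 0.0017 + 0.0033 + 0.0096 = 0.0210. SE = √(0.0210 × (1/43 + 1/100)) = 0.0264.
- Large phase-slope SDs (0.16, 0.15): 0.0256 + 0.0038 + 0.0033 + 0.0096 = 0.0423. SE = 0.0375.

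Type I error is Φ(b/SE − 1.96) + Φ(−b/SE − 1.96), with b = (w1 − w0) × 0.0879.

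| L | ≥40% share | w1 | w0 | w1 − w0 | Bias, ADR points | Ratio of odds ratios | Type I error |
|---|---|---|---|---|---|---|---|
| 10 | 38/133 = 28.6% | 0.116 | 0.050 | 0.066 | 0.13 | 1.005–1.006 | 5.3–5.6% |
| 20 | 33/123 = 26.8% | 0.233 | 0.100 | 0.133 | 0.27 | 1.011–1.012 | 6.1–7.3% |
| 30 | 28/113 = 24.8% | 0.349 | 0.150 | 0.199 | 0.40 | 1.016–1.018 | 7.5–10.1% |
| 40 | 23/103 = 22.3% | 0.465 | 0.200 | 0.265 | 0.53 | 1.022–1.024 | 9.5–14.3% |

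With 120 controls, w1 − w0 is 0.075 to 0.298, or 0.15 to 0.60 points. A 2-point extra fall reverses the sign. With no differential change the bias is zero.

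**4. Regression to the mean alone.** Simulation, 2,500 replicates per scenario; assumed between-facility SD 7 or 12 points, noise SD 1 to 3 points per phase, facilities weighted equally. The bias was −0.02 to +0.02 points with no overlap between stratifying window and pre-phase, +0.02 to +0.23 with half overlap, and +0.04 to +0.43 with full overlap (type I error 5.0 to 8.4%).

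**5. With stratum-by-phase added.** When allocation is random within stratum, the bias in step 2 vanishes. The standard error grows by 1/√(1 − r²), where r is the correlation of the group and lower-stratum indicators: 0.7% (L = 10) to 3.9% (L = 40) with 100 controls, and 1.0 to 5.0% with 120. Colonoscopy-weighted checks gave 0.5 to 5.7%.

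**The case against.** **The wording does not exclude a phase product.** This stands: reading stratum as a main effect is an inference, drawn from the contrast with the moderator and quintile models. If the product was intended, the text should say so.

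**The condition is hypothetical.** This also stands. A reader might infer that the primary estimate is biased, or that low-ADR facilities did improve more. The documents support neither. Nor is any difference in change between strata a sign of confounding: with L = 20, 100 controls and an assumed 4-point CADe effect, mean change would be 0.50 × 4 = 2.0 points in the lower strata and 0.268 × 4 = 1.1 in the upper one from CADe alone, and the planned model would be sound.

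**Large error inflation needs extreme inputs.** Type I error above 20% can be produced, but only with lower-stratum facilities of double volume combined with small slope SDs, or with differential trends of 0.2 to 0.3 log-odds (about 5 to 7.5 points). Nothing in the documents supports either.

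**The plan already has a partial check.** The secondary outcome "Adenoma detection rate stratified by the endoscopist's pre-CADe ADR quintile" brings in a quintile-by-phase term. It works at endoscopist level, is limited to "endoscopists with at least 100 colonoscopies in the pre- and post-deployment phases each will be divided into quintiles based on pre-intervention ADR", and leaves the primary estimate unadjusted. The moderator models name patient and endoscopist characteristics, not facility stratum.

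**The remedy is incomplete.** Selection within the ≥40% stratum was constrained by VISN, so allocation there may vary with VISN size and with devices already placed. A stratum-by-phase term does not address VISN-related trends, and the exact removal of bias in step 5 assumes them away.

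**Conclusion.** The point holds in conditional form. Unequal allocation follows from the plan's own figures for any non-zero number of lower-stratum facilities. The model as written does not protect the group-by-phase estimate against a stratum difference in ADR change that CADe did not cause.

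The size is probably small. Under the assumptions above (2-point differential, equal volume, 10 to 40 lower-stratum facilities, 100 controls) the ratio of odds ratios is about 1.005 to 1.024 under the null. Type I error is about 5 to 12% across most settings, and reaches 14% only with 40 lower-stratum facilities and the smallest slope SDs. Regression to the mean alone adds at most about 0.4 ADR points. Stratum counts, volumes, slope SDs and the differential itself are all assumptions. It should be fixed because the check is cheap and concerns the variable on which allocation depended; confidence is medium.

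**What to change.** - **Primary ADR outcome:** refit the Version 2.1 model with a pre-randomization ADR stratum-by-phase term. Fix the sparsity rule before fitting: merge below 30% with 30 to <40% if either group has fewer than 3 facilities below 30%. Both lower strata had the same planned share, so merging does little harm on average.
- **Status:** outcome data ended June 30, 2023 and Version 2.1 is dated September 10, 2025. Date the addition, label it a sensitivity analysis added after data closure, and report it beside the existing model, which stays primary. Qualify the conclusion if the two differ.
- **Reporting:** tabulate facilities by stratum and group, state the calendar window of the stratifying ADR, and note that VISN-related trends within the ≥40% stratum are not addressed.
- **Other outcomes:** use the term for other binary outcomes only as a further sensitivity analysis. Do not apply it to Provation-only withdrawal time unless enough lower-stratum facilities are present. If the 29 centers with detailed report data are those sites, proportional sampling gives about 29 × 10/143 = 2 to 29 × 40/143 = 8 lower-stratum facilities in both groups together.

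**Cost:** a dated amendment, one or two extra coefficients on data already held, a second reported estimate, and a standard error about 0.5 to 6% larger under the stated assumptions.

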Withdrawal time information will only be available from the subset of VA facilities that use Provation MD software. As withdrawal time is a continuous variable, we will use a linear mixed effects regression model with the same predictors as described above. We will include only those colonoscopies without an associated pathology report and where cecal intubation was complete.

To assess whether the effect of CADe on ADR is moderated by endoscopist ADR quintile, endoscopists with at least 100 colonoscopies in the pre- and post-deployment phases each will be divided into quintiles based on pre-intervention ADR. The quintile variable will be entered into the model described above as a main effect and an interaction (product term) with the group, phase, and group by phase terms.

Computer Assisted Detection of Neoplasia during Colonoscopy Evaluation (CADeNCE)

Study Protocol Version 2.1

September 10, 2025

Evaluation Team:

[name], MHS
[name], MS, MEd
[name], PhD
[name]
[name], MPH

Summary of major revisions:

- 1) In addition to random intercepts for endoscopist and study phase in the regression models, a random intercept for facility was added as this was the unit of randomization

Background:

Colonoscopy is a key diagnostic and therapeutic procedure for the prevention of colorectal cancer (CRC) incidence and mortality. Central to colonoscopy's effectiveness is the identification and removal of colorectal neoplasia, including adenomatous polyps and sessile serrated lesions. The endoscopist's adenoma detection rate (ADR), classically defined as the proportion of screening colonoscopies in which one or more adenomas are detected, has been demonstrated to be strongly inversely associated with their patients' risk of post-colonoscopy colorectal cancer. Therefore, improving adenoma detection is a major target of quality assurance efforts.

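### Patient-level moderator intervals in version 2.1 can be too narrow, because facility-to-facility variation in the moderator-by-phase effect is left out of the model

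*Combined protocol and SAP*

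**What the plan says.** The base model in version 2.1, Statistical Methods, has "random intercepts for facility and endoscopist and random slopes (at the facility and endoscopist level) for study phase", plus fixed effects for group, phase and their product. The Summary of major revisions explains the new facility term: "a random intercept for facility was added as this was the unit of randomization".

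After the main estimate, "we will assess whether the effect was moderated by patient and endoscopist characteristics". Each moderator gets a separate model, with a main effect and "interactions (product terms) with group, phase, and group by phase terms as fixed effects". No random effect for a moderator, or for moderator by phase, is mentioned, and no robust variance.

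The moderator sentence does not list the moderators. The covariate lists in the same section name five patient characteristics (age, sex, race, ethnicity, rurality) and three endoscopist characteristics (specialty, sex, years since degree). Both lists are given as examples. A further analysis has its own paragraph: "To assess whether the effect of CADe on ADR is moderated by endoscopist ADR quintile". It is also item 7 of the Secondary Outcomes: "Adenoma detection rate stratified by the endoscopist's pre-CADe ADR quintile". No significance level, adjustment, ordering or exploratory label is given for any of these tests.

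**The concern.** A patient-level moderator varies within each facility, so every facility supplies its own moderator-by-phase contrast: how much more, or less, detection changed over time in one patient subgroup than in the other. The group by phase by moderator term compares the average of these contrasts between CADe and control facilities. Its error has two parts: binomial noise within facilities, and real variation in the contrast from one facility to the next.

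The planned model contains only the first part. A facility or endoscopist phase slope moves both patient subgroups by the same amount and so cancels from the contrast. With the moderator terms fixed, the second part is set to zero. If it is not zero, the interval is too short and the test rejects too often. What is at stake is a claim that CADe works differently in, say, older or rural patients, reported with more certainty than the facility-level allocation supports.

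**Working it through.** The plan states no figure for these tests, so there is nothing to reproduce. The check asks how large the effect could be.

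**From the documents.** 43 CADe facilities (version 2.1, Intervention). More than 100 controls (given only in version 1.1, Statistical Methods, item 2); 100 is used. Overall ADR 47% (Background); 50% is used, which barely changes the binomial variance.

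**Assumed, not in the documents.** Median 2,000 colonoscopies per facility, three quarters of them pre-deployment, and then half that volume. Facility sizes log-normal with log-SD 0.6. Moderator split 50/50 or 10/90. Facility SD of the moderator-by-phase effect, τ, of 0, 0.05, 0.10 or 0.15 log-odds. Two-sided 5% tests.

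**Step 1. Sampling variance at a median facility.** At ADR 50% each cell of n colonoscopies contributes 4/n to the variance of the log-odds, so v = 4 × Σ(1/n) over the four phase-by-moderator cells.
- 2,000 colonoscopies, 50/50: 4 × (2/750 + 2/250) = 0.0427.
- 2,000 colonoscopies, 10/90: 4 × (1/150 + 1/1350 + 1/50 + 1/450) = 0.1185.
- 1,000 colonoscopies: twice these, 0.0853 and 0.2370.

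**Step 2. True over planned standard error.** The model weights facilities by size. In a group of K facilities the planned variance is v/(1.197K), since the mean size is e^0.18 = 1.197 times the median. Variation between facilities adds τ² × e^0.36/K = 1.433τ²/K. K cancels, so the ratio does not depend on the number of facilities:

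ratio = √(1 + 1.716 τ²/v), where 1.716 = e^0.54.

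**Step 3. Rejection rate when there is no true moderation:** 2 × [1 − Φ(1.96/ratio)].

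| Median volume, split | τ = 0 | τ = 0.05 | τ = 0.10 | τ = 0.15 |
|---|---|---|---|---|
| 2,000, 50/50 | 5.0% | 6.2% | 9.8% | 15.6% |
| 1,000, 50/50 | 5.0% | 5.6% | 7.4% | 10.4% |
| 2,000, 10/90 | 5.0% | 5.4% | 6.7% | 8.9% |
| 1,000, 10/90 | 5.0% | 5.2% | 5.8% | 6.9% |

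In the first row the ratio is 1.05, 1.18 and 1.38 for τ of 0.05, 0.10 and 0.15.

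**Checks.** Simulating 20,000 trials per setting with unequal facilities gave 6.0%, 10.0% and 15.4% for the first row. With equal-sized facilities (1.716 replaced by 1) that row falls to 5.7%, 7.8% and 11.3%. In simulation, facility-robust standard errors brought the rate back to about 5% to 6%. The endoscopist level was not simulated.

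**Number of tests.** With independent tests at 5% and no true moderators, the chance of at least one rejection is 1 − 0.95^8 = 33.7% for the eight named characteristics, and 1 − 0.95^9 = 37.0% with the quintile test.

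**The case against.** The strongest reply is that the omission is a modelling judgement about a higher-order term. Facility and endoscopist intercepts and phase slopes are already present, and they protect the primary comparison. Moderator analyses are commonly fitted this way. The upper end of the range also needs a sizeable τ. At ADR 50%, τ = 0.15 means that the subgroup difference in ADR change spans about ±1.96 × 0.15 × 0.25 = ±7 percentage points across 95% of facilities, and no document supports that. At τ = 0.05 the excess is at most about one percentage point. All of this stands as a limit on size. It does not answer the structural point, because nothing elsewhere in the plan puts this variation into the standard error.

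The argument is also narrower than the full moderator list. For endoscopist characteristics and the ADR quintile, the endoscopist phase slope already covers endoscopist-to-endoscopist variation in the phase effect. Only facility variation in the moderator's own effect stays unmodelled.

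On multiplicity, a label is a reasonable alternative to an adjustment. Apart from the quintile, the moderators are not listed outcomes, no decision is tied to their significance, and the count of eight comes from lists of examples.

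A reader might infer that the plan will call patient-level moderators too often, or that it disregards the unit of randomization. The documents support neither. The first depends on a variance they do not report. The second overlooks the facility terms that version 2.1 added.

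**Conclusion.** The point holds in conditional form. Patient-level moderator intervals can be too narrow, and are if the moderator-by-phase effect differs between facilities. Under the stated assumptions a nominal 5% test rejects about 5.6% to 15% of the time for an evenly split moderator and about 5.2% to 9% for a 10/90 split. The excess is nil at τ = 0 and shrinks with lower volume. Volumes, τ, moderator splits and the 5% level are all assumptions, so the actual size is unknown.

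Multiplicity is secondary. The 34% and 37% assume independent tests at an unstated level. They justify reading the moderator results as exploratory and saying how the quintile result, as a secondary outcome, will be interpreted. They do not show that a formal correction is required. The primary group by phase estimate is not affected.

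**What to change.** In the patient-level moderator models, report standard errors clustered by facility with a small-sample correction (for example EMPIRICAL=MBN in GLIMMIX). A facility-level random moderator-by-phase effect is an alternative where it converges. With binary data and four random terms already in the model it may not, especially for race with several categories, so the clustered errors are the safer default. They also fit the plan's data rule: procedures are kept from one facility per endoscopist, so endoscopists sit within facilities.

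Use one joint test of the three-way terms per moderator. List the moderators, label the analyses exploratory, and state how the quintile result will be read. Holm across the tests is optional and lowers power for any single moderator.

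The cost is some SAP wording and run time, and somewhat wider moderator intervals; if τ is near zero they should widen little. Version 2.1 is dated September 2025 and outcome ascertainment ended in June 2023, so the change should be disclosed as a late one. The primary analysis does not change.

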The NGHP planned to formally evaluate the quantitative and qualitative impact and outcomes of use of CADe within VA medical centers following the purchase and distribution to randomly selected gastrointestinal endoscopy units.

Setting:

Veteran Health Administration (VA) Medical Centers

Intervention:

As part of ongoing quality assurance efforts, the NGHP purchased 115 Medtronic GI Genius® CADe devices in late 2022. All facilities were sorted according to their facility-level ADR (for all indications) and categorized as below 30%, 30% to <40% or ≥40%. A random number generator was then used to sort the VA medical centers within each of these 3 ADR strata. Alternating facilities (i.e., approximately 50%) of facilities within the 2 lower ADR stratum were allocated the CADe devices. To assure equitable distribution of the remaining CADe devices across the 18 VA Integrated Service Networks (VISNs), the remaining devices were offered to randomly selected facilities (all within the ≥40% ADR stratum) such that each VISN had 2-3 facilities with CADe devices.

Upon identification of a potential site, the Gastroenterology Section Chief (or equivalent) at that randomly selected site was asked if they were interested in receiving the devices and if all endoscopists at their facility would agree to use the device during colonoscopy. The physicians were not mandated to use the devices but were asked to notify the NGHP if endoscopists were not routinely using the devices so that the devices could be reallocated to other VA facilities that would make use of the CADe devices. Upon receiving concurrence from facility endoscopy leadership, the devices were installed in all procedure rooms that are routinely used for colonoscopy at that facility. The devices were not installed on travel carts for emergency procedures. One facility did decline to receive the devices due to concerns that the devices would negatively impact efficiency in the endoscopy unit. That facility was replaced with another randomly selected VA medical center. Ultimately, 43 VA facilities received and installed the 115 CADe devices.

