Survey: To assess the end-user experience, a Microsoft Forms electronic survey will be distributed to VA endoscopists who performed at least 25 colonoscopies between December 1, 2022 and May 31, 2023. Endoscopists will be invited via email with up to two follow-up reminders. Survey questions will address self-reported use of CADe for different colonoscopy indications, assessment of the benefits and negative impacts of CADe (e.g., impact on neoplasia detection or withdrawal time), and overall impression of CADe. Survey completion will be optional. Only staff gastroenterologists and surgeons will be eligible to complete the survey.

Oversight:

This quality assurance evaluation was conducted under the auspices of the VA NGHP. Evaluation of the quality of colonoscopy, including the effectiveness of CADe, was previously deemed to be quality assurance by the University of Utah and Salt Lake City VA Medical Center (IRB_00119922); a continuing review of this IRB with amendment was approved for evaluation of AI implementation in 2022. This quality assurance evaluation is registered with ClinicalTrials.gov (NCT05888623).

Database:

The VA Corporate Data Warehouse administrative and patient care data will be used to temporally link CPT codes for colonoscopy to pathology results to assess detection of neoplasia and other study outcomes. Natural language processing (NLP) with full-text indexing searches is used to classify pathology (i.e., adenoma, sessile serrated lesion, adenocarcinoma). Validation of this method to classify adenomas from the pathology results showed 99.5% accuracy.⁷ Separately, colonoscopy data from sites using Provation MD software (Provation, Minneapolis, MN) is exported to a national VA database for quality assurance purposes. This software includes information on colonoscopy quality, such as withdrawal time, indication, bowel preparation quality. Outcomes will be ascertained for colonoscopies performed between October 1, 2021 through June 30, 2023.

Outcomes:

Primary outcome: The primary outcome is the change in ADR from the pre- to post-deployment periods from colonoscopies performed with CADe available compared to colonoscopies performed where CADe was not available.

Secondary Outcomes:

- 1) Adenocarcinoma detection rate
- 2) Sessile serrated lesion detection rate
- 3) Proportion of colonoscopies where pathology specimens are obtained
- 4) Proportion of pathology without adenoma or adenocarcinoma

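### The ADR-quintile analysis requires 100 post-deployment colonoscopies per endoscopist, a condition measured after randomisation that the analysis does not need and that may remove a substantial, unstated share of endoscopists

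*Combined protocol and SAP*

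**What the plan says.** Secondary Outcome 7 in version 2.1 is "Adenoma detection rate stratified by the endoscopist's pre-CADe ADR quintile". The last paragraph of Statistical Methods sets out its analysis: "endoscopists with at least 100 colonoscopies in the pre- and post-deployment phases each will be divided into quintiles based on pre-intervention ADR". The quintile then enters the main mixed model as a main effect and in interactions with group, phase and group by phase.

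That model is a mixed logistic regression with random intercepts and random phase slopes for facility and endoscopist, "with colonoscopy serving as the unit of analysis". Neither the primary analysis nor the other moderator analyses state a minimum volume.

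On timing, the Database section says "Outcomes will be ascertained for colonoscopies performed between October 1, 2021 through June 30, 2023". The Intervention section says that the sponsor bought the "CADe devices in late 2022". Around installation, "the next 5 colonoscopies performed by each endoscopist after the date of installation (or matched date for control sites) will be excluded". Version 2.1 gives no reason for the post-phase minimum, no count of endoscopists that it removes, and no analysis without it.

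**The concern.** The rule has two halves. The pre-phase half limits misclassification of endoscopists into quintiles. The post-phase half does nothing for the quintiles, and a colonoscopy-level model with endoscopist random effects can use endoscopists who have few post-phase procedures.

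The post-phase count is observed after allocation, and CADe could plausibly affect it. One facility declined the devices over worries about efficiency, and Secondary Outcome 5 measures withdrawal time "To assess the negative impact of CADe on procedure time or a possible Hawthorne effect". The documents do not show that volume changes.

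The question at stake is whether CADe works differently for endoscopists with low and high baseline ADR. Under the rule, the answer may come from an undescribed subset weighted towards high volume, with quintile cut-points set inside that subset.

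**Working it through.** The plan states no sample size, power or number of eligible endoscopists for this analysis, so there is no figure to reproduce.

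**1. Does either half of the rule have a purpose?** The overall ADR is 47% (Background). The binomial standard error of one endoscopist's ADR with 100 procedures is √(0.47 × 0.53 / 100) = 0.050, or 5.0 points. This supports a minimum in the phase that defines the quintile, which is the pre phase only.

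**2. Which half binds?** October 2021 to June 2023 is 3 + 12 + 6 = 21 months. If late 2022 means October 2022 at the earliest, the post phase is at most about 9 months. Installation dates are not given, so 6 and 3 months are shown as well. The monthly volume needed is 100 divided by the months in the phase.

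| Post phase | Needed before | Needed after | Ratio |
|---|---|---|---|
| 9 months | 100/12 = 8.3 | 100/9 = 11.1 | 1.3 |
| 6 months | 100/15 = 6.7 | 100/6 = 16.7 | 2.5 |
| 3 months | 100/18 = 5.6 | 100/3 = 33.3 | 6.0 |

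At steady volume the post-phase half is always the stricter one. With a 6-month post phase, an endoscopist who just meets the pre-phase half would have 6 × 6.7 = 40 post-phase procedures. For comparison, the survey goes to "VA endoscopists who performed at least 25 colonoscopies between December 1, 2022 and May 31, 2023", a 6-month window: 25/6 = 4.2 a month. One hundred in 6 months is four times that.

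**3. How many endoscopists might be lost?** This part rests on assumptions: monthly volume is lognormal with log-SD 0.7 and median 12, 18 or 30, it is steady over time, and counts are Poisson (400,000 simulated endoscopists per case). The table shows the share of pre-eligible endoscopists (100 or more before deployment) who also pass the post-phase half, and in brackets the share of their post-phase colonoscopies that is kept.

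| Median a month | 9 months | 6 months | 3 months |
|---|---|---|---|
| 12 | 78% (90%) | 41% (64%) | 9% (24%) |
| 18 | 87% (95%) | 59% (81%) | 20% (44%) |
| 30 | 95% (99%) | 81% (94%) | 45% (71%) |

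With a 6-month post phase, the median volume of those kept is 24.0 a month, against 14.4 for all pre-eligible endoscopists (median 12). For median 18 it is 27.5 against 19.3. If the 5 washout procedures do not count towards the 100, retention falls by a further 1 to 4 points.

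**4. A second set of assumptions.** Take annual volume as lognormal with median 150 to 300 and log-SD 0.5 or 0.8, and require 105 procedures after installation to cover washout. Installation on 1 November 2022 leaves 396 days before and 241 after. The volume needed is 100/396 × 365.25 = 92 a year before and 105/241 × 365.25 = 159 after, and 9% to 46% of pre-eligible endoscopists are lost. Installation on 1 January 2023 leaves 457 and 180 days. The volume needed is 80 and 213 a year, and 24% to 73% are lost.

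**5. How large could a difference between groups be?** In the simulation of step 3, a 5% fall in post-phase volume under CADe lowers retention by 1 to 4 points: for example 40.7% to 37.4% (median 12, 6 months) and 95.4% to 94.3% (median 30, 9 months).

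**The case against.** A symmetric minimum is a recognisable choice. The question is change between phases, and an endoscopist with very few post-phase procedures says little about their own change. This is true, but the mixed model already gives such endoscopists little weight, so it does not require their removal.

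The selection argument is limited. Control sites have matched dates, so losses from late installation fall in both groups. Bias in the quintile interaction would need CADe to change volume, and the endoscopists lost to respond differently within quintile. Neither is shown, and withdrawal time at Provation sites is only indirect evidence about volume. This stands, and it keeps the point to a modest one.

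The volume distributions have no source in the documents, and 9% to 95% is a very wide range. Counting endoscopists also overstates the information lost: with a 6-month post phase, 64% to 94% of post-phase colonoscopies remain. Both points stand. They limit what can be said about size, but not the finding that the condition is unneeded and unexplained.

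Finally, with a pre-phase minimum alone, endoscopists who leave before the post phase would still help set the cut-points. That is so, but those cut-points are defined at baseline, and such endoscopists can be counted and reported.

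**Conclusion.** The concern holds. The post-phase minimum is needed neither to form the quintiles nor to fit the model, and it makes a listed secondary outcome depend on a count observed after randomisation. At steady volume it is the binding half of the rule for every post-phase length considered, by a factor of 1.3 to 6.0. That result needs only the dates and the steady-volume assumption. The share of endoscopists removed is unknown. It could be small or very large, and the percentages above illustrate assumed volumes.

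The likely consequences are lost precision and a result that applies mainly to higher-volume endoscopists. Differential selection is possible but likely modest. The primary ADR analysis and the other moderator analyses have no such threshold and are unaffected. The change should be made. Confidence is medium, because installation dates and volumes are not given.

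**What to change.** Replace the eligibility sentence with:

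> Endoscopists with at least 100 pre-deployment colonoscopies will be divided into quintiles based on pre-intervention ADR. All their post-washout colonoscopies will be included, whatever the post-phase count.

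Report, by group and quintile, how many endoscopists have no or few (for example fewer than 20) post-phase colonoscopies. Keep the rule of 100 in both phases as a sensitivity analysis with the same quintile cut-points, so that no planned result is lost.

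The cost is one SAP sentence, one count table and one extra model run on data already held. The small downside is that any display of post-phase ADR for single endoscopists will be noisier where they contribute few procedures.
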